6.3 KEY DEFINITIONS AND LABELS

6.3.1 Baseline Values

Unless otherwise specified, the last observed measurement prior to the dose of trial vaccine will be considered the baseline measurement.

6.3.2 Study Day

Study Day is the number of days since the administration of the study vaccine, which is counted as Study Day 0. If the assessment date is after the date of the first vaccination, the study day is calculated as date of assessment - date of the first dose administration + 1. If the assessment date is prior to the date of the first vaccination, the study day is calculated as date of assessment - date of the first dose administration.

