5.3 PER PROTOCOL SET

The Per Protocol (PP) set will consist of the subjects with no major deviations related to the analyses and with Day 0 and Day 21 immunogenicity assessments. Subjects who had blood samples for immunogenicity collected outside of the time window are to be excluded from the PP set. Subjects who received the wrong vaccine, but for whom the treatment received can be unequivocally confirmed, will be analyzed in the PP set as treated, provided they have no other deviations that could compromise their data. The PP set will be the primary analysis population for the primary immunogenicity endpoint.

Statistical Analysis Plan

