6. GENERAL ASPECTS FOR STATISTICAL ANALYSIS

6.1 SUMMARY STATISTICS

The standard summary statistics that will be calculated for quantitative and qualitative variables are:

- Quantitative: number of subjects (N), mean, standard deviation (SD), median, minimum and maximum of the raw data
- Qualitative: number of subjects (n), absolute and relative frequencies (%) per category

A subject who is randomized but does not receive study drug will be included in the subject data listings. All pre- and post-vaccination results, including repeated and unscheduled assessments, will be included in the data listings. Data collected at unscheduled visits that occurred outside the time windows specified in the protocol will be included in the data listings but will not be included in the analyses.

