6.3.3 Onset day

Onset day is calculated as date of event – date of the first vaccination +1.

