9.1.2 Collection Schedule

Solicited local and systemic reactions will be collected from the time of vaccination through Day 7. Any solicited local or systemic reactions lasting beyond Day 7 will be considered an AE with a start date 8 days post-vaccination.

Solicited local and systemic reactions occurring within 15 minutes post vaccination will be considered as Immediate Complaints.

All AEs occurring within 21 days after vaccination will be recorded in the source documents or MA and reported in the “Adverse Event” form in the subject’s eCRF, irrespective of intensity or whether or not they are considered to be vaccination-related.

The SAEs and NOCDs will be followed up until complete resolution or stabilization.

Statistical Analysis Plan

Follow-up of unresolved SAEs, AEs leading to withdrawal, or NOCDs after the end of the study period will continue under the discretion of the Investigator.

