9.1.3 Derived and Imputed Data

Every attempt will be made to get complete dates and times or best estimates for AEs which may occur or start outside of the clinic. AEs which begin during the subject's stay in clinic are expected to have complete dates and times. Incomplete AE dates and times will not be imputed.

There is no imputation in cases where severity or relationship information is missing for TEAEs.

Days from vaccination are calculated as date of event – date of vaccine +1.

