- Summary of severe and potentially life-threatening related TEAEs by MedDRA SOC and PT.
- Summary of serious TEAEs by MedDRA SOC and PT.
- Summary of NOCDs by SOC and PT.

Statistical Analysis Plan

The following summary of hypersensitivity events will be presented by vaccine lot and overall:

- Summary by MedDRA SOC and PT.

AEs will be listed by subject, treatment (lot) and day of onset for all AEs. Solicited reactions including Immediate Complaints will be displayed in Listing 16.2.7.1. Unsolicited AEs will be listed in Listing 16.2.7.2, NOCDs will be listed in Listing 16.2.7.4, and hypersensitivity will be listed in Listing 16.2.7.5.

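### SAP 6.3.2 counts vaccination as Study Day 0 but adds 1 to every later date, so Study Day 1 cannot occur, day 21 becomes 22, and onset day disagrees on the vaccination date

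*SAP*

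**What the plan says.** SAP 6.3.2 opens with a definition: "Study Day is the number of days since the administration of the study vaccine, which is counted as Study Day 0". It then gives two formulas. For a date after vaccination, "the study day is calculated as date of assessment - date of the first dose administration + 1". For a date before vaccination, it is the plain difference with no offset. The vaccination date itself is covered only by the opening definition.

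Two further derivations use the same offset. Onset day in SAP 6.3.3 is the event date minus the "date of the first vaccination +1". Days from vaccination in SAP 9.1.3 is the event date minus the "date of vaccine +1". Neither makes an exception for the vaccination date.

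The schedule in both documents (Table 1 of the protocol and Table 1 in SAP 3.8) is zero-based: vaccination on Day 0, phone contacts on Day 1 (+1) and Day 8 (-1/+1), and the second blood sample on Day 21 (-2/+3). The row carrying these day numbers is labelled Study Day.

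Three other places bear on the point:

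- SAP 9.1.2: a solicited reaction lasting beyond Day 7 "will be considered an AE with a start date 8 days post-vaccination".
- SAP 9.1.6: "AEs will be listed by subject, treatment (lot) and day of onset for all AEs".
- SAP 5.3: "Subjects who had blood samples for immunogenicity collected outside of the time window are to be excluded from the PP set".

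**The concern.** A count of days since an event cannot equal the date difference plus one. A programmer working from 6.3.2 must follow either the definition or the formula, and two programmers could choose differently. Following the formula moves every derived post-vaccination day off the protocol's scale, and the vaccination date receives two different numbers depending on which variable is used.

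The direct consequence is in derived study days and onset days, including adverse event listings organised by day of onset. The possible consequence is larger. The PP set is the primary analysis population for lot consistency, and membership depends on whether the Day 21 sample was taken in its window. SAP 5.3 does not say on which day scale that is checked. SAP 6.1, on unscheduled visits, refers to data "outside the time windows specified in the protocol", and SAP 7.3 lists visit window as a deviation category, but neither says how the day is computed.

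**Working it through.** Let d be the vaccination date subtracted from the assessment or event date, so d = 0 on the vaccination date.

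**Formulas**

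- SAP 6.3.2 definition: Study Day = d.
- SAP 6.3.2 formula: Study Day = d if d < 0; 0 if d = 0 (from the definition); d + 1 if d > 0.
- SAP 6.3.3 and 9.1.3: onset day, or days from vaccination, = d + 1 for every d.

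**Values**

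| d (definition and schedule) | Study Day by 6.3.2 formula | Onset day / days from vaccination |
|---|---|---|
| -1 | -1 | 0 |
| 0 | 0 | 1 |
| 1 | 2 | 2 |
| 7 | 8 | 8 |
| 8 | 9 | 9 |
| 18 | 19 | 19 |
| 19 | 20 | 20 |
| 21 | 22 | 22 |
| 23 | 24 | 24 |
| 24 | 25 | 25 |

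**Results**

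1. Evaluated for d from -30 to +30, the 6.3.2 formula skips exactly one value, Study Day 1. A call made on the scheduled Day 1 cannot have that derived day; it becomes 2.
2. For every d > 0 the formula exceeds the definition by 1: 1 becomes 2, 8 becomes 9, 21 becomes 22.
3. Study Day and onset day agree for all d > 0. They differ by 1 on the vaccination date (0 against 1) and before it (for example -1 against 0).
4. The start date assigned in SAP 9.1.2 is d = 8. SAP 9.1.3 gives the same date as 8 + 1 = 9 days from vaccination.

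**Sampling window, if checked with the 6.3.2 variable**

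- Window on the schedule: 21 - 2 = 19 to 21 + 3 = 24, so d = 19 to 24, which is 6 days.
- Derived Study Day between 19 and 24 means d + 1 between 19 and 24, so d = 18 to 23.
- The two ranges share d = 19 to 23, which is 5 of the 6 days. Day 24 is lost and day 18 is gained: 24 + 1 = 25 falls outside, and 18 + 1 = 19 falls inside.

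**Check of the remedy**

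With the + 1 removed everywhere, all three variables equal d. Vaccination is 0, the phone contacts are 1 and 8, the visit is 21 and the window is 19 to 24. All match Table 1, with no gap.

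**The case against.** The strongest reply is that no planned result is shown to change.

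- The primary ANCOVA (SAP 8.1.6) uses lot and baseline titer, not study day.
- The secondary immunogenicity parameters use the Day 0 and Day 21 titers.
- Treatment emergence is decided by comparing dates and times (SAP 9.1.1).
- Most safety parameters use the eCRF visit label (SAP 6.5).
- Solicited reactions come from fixed daily diary columns.

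All of this stands, and it limits the reach of the error.

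It can also be said that 9.1.6 may only set a sort order, which a uniform + 1 leaves unchanged for post-vaccination events. Listings show the recorded dates (SAP 6.4), so the true interval can be recovered. Onset day is defined only by its formula, so taken alone it contradicts no stated definition. An event dated the day before vaccination is hardly to be expected, because screening and vaccination share one visit. These points are fair. They bear on how visible the error would be, not on whether the rule is wrong.

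The last reply is that nothing ties the PP window to 6.3.2, because Table 1 already fixes it on a Day 0 schedule. This holds only in part. No text says the window is checked with the derived variable. But Table 1 in the SAP labels its day row Study Day, the very term that 6.3.2 defines, so a literal reader has a direct route from the window to the faulty formula.

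**Conclusion.** The error is real and follows from the SAP's text alone, without any outside assumption. The 6.3.2 formula contradicts the definition beside it. Every post-vaccination Study Day is exactly 1 too high, and Study Day 1 cannot occur. Onset day and days from vaccination are also 1 above the protocol's scale, including on the vaccination date, where they disagree with Study Day.

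The effect on the primary analysis set is conditional. It arises only if the programs check the Day 21 window with the 6.3.2 variable. In that case valid day-24 samples would be excluded from the PP set and out-of-window day-18 samples would be kept. The documents give no distribution of sampling days, so the number of subjects cannot be derived. Neither treatment emergence nor the Day 0 to 7 solicited summaries are shown to depend on the formula, and there is no basis for saying that the lot-consistency conclusion would change.

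This should be corrected: a stated derivation rule gives wrong values, and the correction is unambiguous.

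**What to change.** - Delete the + 1 in SAP 6.3.2, 6.3.3 and 9.1.3, so that Study Day, onset day and days from vaccination all equal the assessment or event date minus the vaccination date, with vaccination as 0.
- Add to SAP 5.3: *The Day 21 blood-sample window is 19 to 24 elapsed days after the vaccination date.*

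The cost is three formula edits, one sentence and the matching derivation lines in the programs. The SAP is final version 1.0, so a new version is needed, and any output already programmed with the + 1 must be rerun. No new data are needed. SAP section 5 has subjects assigned to analysis sets before database lock and unblinding, so the correction belongs before that step.

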6.3.3 Onset day

Onset day is calculated as date of event – date of the first vaccination +1.

6.4 MISSING DATA

Subjects who withdraw from the study will have all data listed and, wherever relevant, included in any subject summaries. No imputation of values for missing data will be performed.

Adverse events and concomitant medications with missing assessment times will have imputed times for the purposes of calculation of relativity to study vaccine or duration. However, the assessment times (start date, stop date) without imputation will be presented in the listings.

For the start of a concomitant medication or adverse event:

- Only the year is reported: If the subject received the study vaccine in the year reported, then the date of the first injection of study vaccine will be used as the start date; otherwise January 1 of the year reported will be used as the start date.

Statistical Analysis Plan

- The month and year are reported: If the subject received study vaccine in the month and year reported, then the date of the first injection of study vaccine will be used as the start date; otherwise the first day of the month and year will be used as the start date.
- The time is missing: If the start date, either actual or estimated, is the same as the date the subject started receiving study vaccine or experienced the adverse event, then the time of the first injection of study vaccine will be used as the start time; otherwise 00:00 will be used as the start time.

For the end of a concomitant medication or adverse event:

- If the adverse event or concurrent medication continues after the last study contact date, then no stop date or time will be estimated.
- Only the year is reported: The earlier of December 31 of the year reported and the date of the last study contact with the subject will be used as the stop date.
- The month and year are reported: The earlier of the last date of the month and year reported and the date of the final contact with the subject will be used as the stop date.
- The time is missing: 23:59 will be used as the stop time

6.5 VISIT WINDOWS

In general, all safety data will be summarized by scheduled visits based on the scheduled events indicated in Table 1. The visits indicated on the eCRF (i.e. eCRF visit) will be used as the analysis visits for analysis of most safety parameters. The following rules will apply unless other handling is specified for a particular analysis.

- For repeatable safety assessments collected at scheduled time points pre-vaccination, the last usable value will be used in by-time point analyses but all values will be included in the listings.
- For repeatable safety assessments collected at scheduled time points post-vaccination and at follow-up, the first usable value for the time point will be used in by-time point analyses but all values will be included in the listings
- If a patient has no record in an analysis window, the patient will be considered missing at that time point.

1009513

MEDICAGO R&D Inc.

CP-PRO-QVLP-011

Final version 1.0, 24JAN2018

Statistical Analysis Plan

6.6 POOLING OF CENTERS

No center pooling will be employed.

Statistical Analysis Plan

7. DEMOGRAPHIC, OTHER BASELINE CHARACTERISTICS AND MEDICATION**7.1 SUBJECT DISPOSITION AND WITHDRAWALS**

The following frequencies (number and percent) will be displayed based on the vaccinated subjects:

- Screened Subjects (numbers only)
- Screen Failures (numbers only) and reason for screen failure
- Randomized Subjects (numbers only)
- Vaccinated Subjects
- Subjects in the Safety Analysis Set
- Subjects in the Full Analysis Set
- Subjects in the Per Protocol Set
- Subjects who completed the study (Day 21)
- Subjects who withdrew early from study (Day 21) and reason for withdrawal

The denominators for the percent calculations will be the number of subjects vaccinated, whether or not they are included in any of the analyses.

Subjects' completion/discontinuation status will be listed, including subject identifier, date of completion/early discontinuation and, for those who discontinued early, the specific reason(s) for discontinuation.

Inclusion/exclusion criteria definitions and deviations will be listed. If no inclusion/exclusion criteria are reported, this will be noted in place of the listing.

A listing of subjects excluded from the analysis sets will also be produced.

7.2 DEMOGRAPHIC AND OTHER BASELINE CHARACTERISTICS

Demographic data will be displayed in listings and summarized by vaccine lot (treatment group). Continuous variables including age, weight, height and BMI will be summarized with N, Mean (SD), Median, Min and Max. Count and percentage of subjects will be presented for categorical variables such as sex, race, and ethnicity.

Statistical Analysis Plan

7.3 PROTOCOL DEVIATIONS

Protocol deviations will be reviewed by Medicago (or its designee) to identify any non-compliances likely to have a significant effect on the safety and rights of a subject or the reliability and robustness of the data generated. These deviations will be included in the clinical study report.

All protocol deviations related to study inclusion or exclusion criteria, conduct of the trial, subject management or subject assessment will be listed and assessed during the course of the study. The list of protocol deviations will be finalized before database lock.

The protocol deviations will be grouped into different categories which may include, but are not limited to:

- Eligibility criteria
- Visit window
- Informed consent procedure
- Prohibited medication
- Administration/dispensing of vaccine
- Failure to report SAE or Pregnancy within specified timelines
- Biological sample procedures
- Assessments procedures
- Other

A summary table of protocol deviations by vaccine lot and category will be provided.

7.4 MEDICAL HISTORY AND CONCOMITANT DISEASES

Medical histories will include grade of medical condition, if they are ongoing. Medical history abnormalities will be coded to Medical Dictionary for Regulatory Activities (MedDRA[®]) terms, using version 20.0. All findings on medical history will be evaluated by the investigator for clinical significance.

Medical history findings will be summarized by system organ class (SOC) using internationally agreed order and listed by subject.

Statistical Analysis Plan

7.5 PRIOR AND CONCOMITANT MEDICATIONS

Any new or changed medications reported by the subject post-vaccination and through to the end of the study will be recorded in the electronic case report form (eCRF) as a concomitant medication. Any AEs associated with the new or changed medication use must also be documented.

Medications must be reported in the eCRF (reason for use, dates of administration, dosage, frequency, and route) if the use meets the following conditions:

- Within 30 days preceding vaccination: any treatments and/or medications specifically contraindicated (e.g. influenza vaccines, any immunoglobulins or other blood products, or any immune modifying drugs, etc.);
- From randomization to Day 21, inclusive: any medication (including, but not limited to, over-the-counter medicines such as aspirin or antacids), vitamins, and mineral supplements;
- Any concomitant medication use to treat conditions reported as medical history;
- Any investigational medication or vaccine; any vaccine not foreseen in the study protocol.

The use of prophylactic medications to prevent or pre-empt symptoms due to vaccination is specifically prohibited up to Day 7.

The original verbatim terms (entered in the case report form (CRF) for prior and concomitant medications) will be coded using the World Health Organization Drug Dictionary (WHO DD), March 2017, into drug class (up to anatomical therapeutic chemical (ATC) level 4) and preferred term.

Prior and concomitant medication data will be summarized by ATC level 1 and level 3, and listed chronologically by subject including all data collected in the eCRF (eCRF), along with coded variables (ATC and Preferred Term) and other related variables (e.g., start/stop date, dose). If no prior or concomitant medications are reported, this will be noted in place of the listing.

7.6 TREATMENT EXPOSURE

Vaccine administration data will be shown in listing.

Statistical Analysis Plan

8. IMMUNOGENICITY ANALYSIS**8.1 PRIMARY IMMUNOGENICITY ENDPOINT AND ANALYSIS****8.1.1 Datasets analyzed**

Immunogenicity analysis (GMTs and GMT Ratios) will be based on the PP set, and repeated using the FAS as the sensitivity analysis.

8.1.2 Measurements

Immunogenicity will be evaluated by measuring the serum antibody response induced in subjects, using the HI test against the homologous vaccine strains. HI antibody response will be measured using titer values.

The homologous influenza strains are as below:

1. A/California/7/2009 (H1N1)
2. A/Hong Kong/4801/2014 (H3N2)
3. B/Brisbane/60/2008 (B/Brisbane)
4. B/Phuket/3073/2013 (B/Phuket)

8.1.3 Scheduled Collection

Immunogenicity data will be collected on Days 0 and 21.

8.1.4 Derived and Imputed Data

- For the purpose of endpoints calculation, all HI antibody responses below the lower limit of quantitation (BLQ, <10) will be attributed a value of 5.
- GMT and 95% confidence intervals for the vaccine lots are calculated as the antilog of the mean and 95% confidence limits of log (base 10) transformed total titer values.
- GMT Ratios and 95% confidence intervals for the pairwise comparisons of the lots are calculated as the antilog of the differences of the means and 95% confidence limits of log (base 10) transformed total titer values.

8.1.5 Data Summarization

The adjusted Day 21 GMTs and the lot-to-lot adjusted Day 21 GMT ratios will be summarized by the vaccine lots and by homologous influenza strains. Mean and 95% CIs

Statistical Analysis Plan

will be calculated for the adjusted Day 21 GMTs and GMT ratios. Reverse cumulative distribution curves of HI titers will be plotted.

8.1.6 Model Fitting

Analysis of log (base 10) transformed titer will be performed using Analysis of Covariance (ANCOVA) with vaccine lot as main effect and baseline titer as covariate. Pairwise comparisons between each vaccine lot will be performed using two-sided, 95% CIs on the vaccine lot differences in GMTs, based on the least-squares mean differences from the ANCOVA model.

The model is shown below:

```
Proc mixed data=ADZ (with the appropriate pooled subset);
  class trtpn;
  model aval= trtpn Base;
  Lsmeans trtpn/ diff cl alpha=0.05;
  Ods output LSMEANS=_outmix DIFFS =_outdiff;
  run;
  Quit;
  Data outdiff;
  Set outdiff;
  GMTR = 10**(Estimate); *GMTR: GMT Ratio;
  GMTR_LCL = 10***(Lower); *GMTR_LCL: GMT Ratio 95%CI lower limit;
  GMTR_UCL = 10***(Upper); *GMTR_UCL: GMT Ratio 95%CI upper limit;
  Run;
```

where aval is the \log_{10} transformed titer values.

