1.3 Clinical Studies

Under the clinical development program for the Quadrivalent VLP Influenza Vaccine, Medicago has conducted five clinical trials to date (CP-Q12VLP-004, CP-Q13VLP-007, CP-Q13VLP-008, CP-Q14VLP-009, and CP-Q14VLP-010). Study designs and statuses are summarized in [Table 2](#).

Table 2 Summary of Design of Clinical Studies Performed to Date with the Quadrivalent VLP Influenza Vaccine

Study / Status	Phase	Design	Population	N	Treatment groups
CP-Q12VLP-004 / Completed	1-2	Single-center, observer-blind, randomized, dose-ranging, placebo-controlled study	Healthy adults 18-49 years of age, both genders	90 (active; ratio 1:1:1); 30 (placebo)	3 µg VLP; 9 µg VLP; 15 µg VLP; placebo
CP-Q13VLP-007 / Completed	2A	Multicenter, observer-blind, randomized, dose-ranging, placebo-controlled study	Healthy adults 18-49 years of age, both genders	225 (active; ratio 1:1:1); 75 (placebo)	15 µg VLP; 30 µg VLP; 60 µg VLP; placebo
CP-Q13VLP-008 / Completed	2	Multicenter, observer-blind, randomized, dose-ranging, placebo-controlled study	Healthy subjects of 50 years of age or older, both genders	375 (active; ratio 1:1:1:1); 75 (placebo)	15 µg VLP; 30 µg VLP; 60 µg VLP; 7.5 µg VLP + Alhydrogel®; 15 µg VLP + Alhydrogel®; placebo
CP-Q14VLP-009 / Clinic portion completed	2	Multicenter, observer-blind, randomized, dose ranging, active-comparator clinical study	Healthy adults aged 18 - 64 years, both genders	604 (active; ratio 1:1); 296 (active comparator)	15 µg VLP; 30 µg VLP; 15 µg/strain dose of FluLaval® Tetra
CP-Q14VLP-010 / Clinic portion completed	2	Multicenter, observer-blind, randomized, dose ranging, active-comparator clinical study	Healthy subjects of 65 years of age or older, both genders	499 (active; ratio 1:1); 250 (active comparator 1); 252 (active comparator 2)	30 µg VLP; 60 µg VLP; 15 µg/strain dose of FluLaval® Tetra; 60 µg/strain dose of Fluzone® High Dose

Overall, a total of 1,793 normal healthy subjects have received a single dose of the Quadrivalent VLP Influenza Vaccine: 1,106 subjects aged from 18 to 64 years and 687 subjects 65 years of age and older.

An overview of the available safety and immunogenicity findings from these studies are summarized in Section 1.3.1 and Section 1.3.2, respectively. For detailed information on these findings, please refer to the current version of the IB.

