6 TREATMENT ALLOCATION AND BLINDING

6.1 Randomization

Randomization will be stratified by site. Subjects will be randomized to one of three treatment groups, based on a computer-generated randomization schedule prepared by or under the supervision of Medicago before the study. The randomization system will assign the treatment group.

Potential study subjects will be screened and assigned a subject number. Once all Screening procedures, including Day 0 pre-randomization procedures, have been completed and the study eligibility is confirmed by the Investigator, the randomization numbers will be allocated to subjects within the appropriate treatment group by the randomization system.

Once a randomization number has been assigned, it will not be re-used for any reason. No subjects will be randomized into the study more than once. If a randomization number is allocated incorrectly, no attempt will be made to remedy the error once the study vaccine has been dispensed: the subject will continue on the study with the assigned randomization number and associated treatment. The study staff will notify the Sponsor Contact as soon as the error is discovered. Admission of subsequent eligible subjects will continue using the next unallocated number in the sequence.

The randomization number and treatment will be recorded along with the six-digit subject number for each subject in the investigational product accountability log.

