12.2 Sample Size Determination

Based on data from the CP-Q14VLP-009 study, a sample size of 400 subjects per lot (a total of 1,200 subjects) will have a greater than 90 % power to test the consistency criterion between the lots (i.e. to test that the pairwise comparisons of the two-sided 95 % CI limit for adjusted GMT ratios of the three lots being tested [lot 1/lot 2, lot 1/lot 3, lot 2/lot 3] fall within the equivalence range of 0.67 to 1.5 for all four vaccine strains).

A drop-out rate and exclusion from the PP set of approximately 10 % was assumed in the sample size calculation.

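### Site stratifies the randomisation but is absent from the primary ANCOVA, and the scale of the baseline covariate is not stated; the cost is modest power, not validity

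*SAP*

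**What the plan says.** Protocol 6.1 states "Randomization will be stratified by site", and SAP 3.6.1 repeats it. The primary analysis in SAP 8.1.6 regresses log10 Day 21 titer using "Analysis of Covariance (ANCOVA) with vaccine lot as main effect and baseline titer as covariate". The code matches the text: the model line is "model aval= trtpn Base", only the lot variable is in the `CLASS` statement, and there is no `RANDOM` statement. SAP 6.6 says "No center pooling will be employed", which settles how centers are grouped but does not bring them into the model. Protocol 12.3.1 names an ANCOVA without listing covariates.

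On the covariate, SAP 8.1.6 defines `aval` as the log10 titer but gives no scale for `Base`. SAP 6.3.1 fixes only its timing: "the last observed measurement prior to the dose of trial vaccine will be considered the baseline measurement". SAP 8.1.4 sets HI values below 10 to 5, again without giving the covariate's scale.

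**The concern.** A factor used to stratify randomisation would normally appear in the primary model. When it is left out, the lot estimates remain unbiased, but the standard error is computed as if site had not been balanced. Consistency requires all 12 intervals (3 lot pairs by 4 strains) to lie inside 0.67 to 1.5, and SAP 8.1.7 tests them in a fixed order that stops at the first failure. Interval width therefore bears directly on the chance of success, and any excess width is power given up for nothing.

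The undefined covariate is a different kind of gap. Two programmers following the same SAP, one using raw and the other log10 baseline titers, would obtain different primary intervals.

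**Working it through.** **Inputs from the documents.** 400 subjects per lot, about 10% loss from the PP set (Protocol 12.2), so 400 × 0.9 = 360 per lot and 1,080 in total. Two-sided 95% intervals, margins 0.67 and 1.5, that is log10(0.67) = −0.1739 and log10(1.5) = 0.1761. Residual degrees of freedom for lot plus one covariate: 1,080 − 4 = 1,076.

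**Assumed, because the documents do not give them.** Residual log10 SD; 6 to 15 sites; site share of residual variance of 0, 2, 5 or 10%; independent strains; true lot ratios of 1.

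**The plan's own figure.** The stated power above 90% cannot be reproduced, since neither an SD nor a true ratio is given. With 360 per lot it holds for all 12 intervals if the SD is at most about 0.52 with true ratios of 1, about 0.49 if one lot differs by a factor of 1.05, or about 0.43 if one lot differs by 1.10.

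**Interval width.** With many sites, the ratio of interval widths (site omitted / site included) is 1/√(1 − share). With S equal sites only (S − 1)/S of the site variance is realised, so the excess is slightly smaller. Simulation (2,000 trials per setting, blocks within site) gave the second column below. The actual sampling SD of the estimator was the same with and without site (0.0351 for both at a 10% share with total SD 0.5), so the extra width is pure overstatement of the SE.

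**False-claim rate at a margin.** With site omitted, the one-sided error is Φ(−1.96/√(1 − share)).

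| Site share | Excess width, 6–15 sites | Excess width, many-site limit | One-sided error, site omitted |
|---|---|---|---|
| 0% | 0% | 0% | 2.5% |
| 2% | 0.8–1.0% | 1.0% | 2.4% |
| 5% | 2.1–2.5% | 2.6% | 2.2% |
| 10% | 4.5–5.0% | 5.4% | 1.9% |

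**What this does to one comparison.** At within-site SD 0.515 the SE is 0.515 × √(2/360) = 0.0384. The half-width is 1.962 × 0.0384 = 0.0753, leaving 0.1739 − 0.0753 = 0.0986, or 2.57 SE, before the lower limit reaches 0.67. With site omitted at a 10% share the half-width becomes 0.0753 × 1.054 = 0.0794, leaving 0.0945, or 2.46 SE.

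**Joint power for all 12 intervals**, using the many-site limit for the inflation:

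| SD assumption | With site (2/5/10% share) | Site omitted (2/5/10% share) |
|---|---|---|
| Within-site SD 0.45 | 98.7% throughout | 98.6 / 98.5 / 98.1% |
| Within-site SD 0.50 | 93.3% throughout | 92.9 / 92.2 / 90.9% |
| Within-site SD 0.515 | 90.1% throughout | 89.6 / 88.7 / 86.9% |
| Total SD 0.50 | 94.2 / 95.3 / 96.9% | 93.9 / 94.6 / 95.7% |
| Total SD 0.515 | 91.2 / 92.9 / 95.1% | 90.8 / 91.8 / 93.3% |

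The first three rows add site variance on top of the stated SD. The last two treat the stated SD as already containing it.

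**Scale of the covariate.** If `Base` is log10, nothing changes. If it were run raw, the SE ratio is √((1 − R²raw)/(1 − R²log)). With two-fold titers, baseline log10 mean 1.0 to 1.4 and SD 0.4 to 0.6, intervals would be 1–3% wider at an assumed log-log correlation of 0.3, 4–9% at 0.5 and 10–23% at 0.7. A separate simulation at correlation 0.5 gave 0.1556/0.1463, about 6% wider, with coverage still close to 95%.

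**The case against.** The omission cannot produce a false claim of consistency; the only party at risk is the sponsor, through its own power. Nothing in the documents supports a large site effect. The trial runs in one country, in adults aged 18 to 49 with no influenza vaccine in the previous 24 months. Sera go to the analytical laboratory for HI testing, and the Day 0 titer is already a covariate.

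The 3-point loss also comes from the least favourable setting: a within-site SD chosen so that power is exactly 90%, with site variance added on top. The sample size was "Based on data from the CP-Q14VLP-009 study, a sample size of 400 subjects per lot", and Protocol Table 2 describes that source study as "Multicenter, observer-blind, randomized, dose ranging, active-comparator clinical study". Its SD may therefore already include site variance, in which case planned power stays above 90%. Using the simulated 4.5–5.0% inflation instead of the 5.4% limit gives 87.2–87.4% in place of 86.9%, and correlated strains narrow the gap a little further (91.4 versus 88.8% at an assumed correlation of 0.5).

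Finally, a log10 baseline is the natural reading of SAP 8.1.6.

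All of this is fair, and it limits the weight of the point. It does not explain why the stratification factor is left out, and the SAP gives no reason. The natural reading of `Base` is still not a written one.

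**Conclusion.** The point holds. The primary model omits the factor by which the trial randomises, and the scale of its covariate is unstated. The omission is conservative. Over site shares of 0 to 10% it makes the intervals 0 to about 5% too wide and costs 0 to about 3 points of joint power. If the planning SD is a total SD of 0.515, adding site would gain 0.4 to about 1.8 points, with no shortfall either way. If site is not prognostic, nothing is lost. These sizes rest on assumed SDs, site counts and site shares, and the documents do not show that the stated power fails. A positive result under the current model would stand.

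The covariate point is a gap in specification, not a demonstrated error. It affects reproducibility and precision, not coverage. Both should be corrected because they concern the primary analysis and the correction is nearly free.

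**What to change.** In SAP 8.1.6, specify log10(Day 21 titer) = lot + site + log10(Day 0 titer). Add site to the `CLASS` and `MODEL` statements as a fixed effect, one level per site with no pooling. This agrees with SAP 6.6 and needs no size threshold to be chosen later; a site with a single PP subject simply contributes nothing to the lot contrasts. Define `Base` as log10 of the Day 0 titer, with values below 10 set to 5. Use the same model for the FAS repeat in SAP 8.1.1. If the sponsor prefers to leave site out, the SAP should say why, and `Base` should be defined in any case.

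The cost is SAP wording and one model term, fixed before unblinding, with no new data. Protocol 12.3.1 lists no covariates, so the change does not contradict it. If site truly has no effect, intervals widen by about 0.001% with 10 to 15 equal sites, 0.06% with five additional sites of 4 subjects, and 0.24% with ten additional sites of 2 subjects. Only a few of the roughly 1,076 degrees of freedom are used.
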